## 14.0 Body Fluid Biospecimens

### 14.1 Summary Table of Research Blood/Blood Products to Be Collected for This Protocol

Indicate if specimen is mandatory or optional	Collection tube description and/or additive (color of tube top)	Volume to collect per tube (number of tubes to be collected)	Blood product being processed and submitted by participating site	Pre-Treatment (prior to starting placebo or selumetinib)	Additional processing required at site after blood draw?	Storage /shipping conditions 
Mandatory	Lavender	10 ml (1)	Blood	X	No	Refrigerated

(Requisition form located on the ACCRU web site.)

[figure not shown]
14.2 No kits will be required for this study.

14.3 Samples should be collected Monday through Thursday. However, if the subject can only be seen on Friday, notify the Biospecimen Resource Manager listed in the protocol resource page of the sample, study ID and tracking number and Saturday arrangements will be made to stabilize the sample over the weekend. Do not collect specimens the day before a federal holiday. NOTE: Research blood samples should not be collected and submitted until *after* the patient is registered onto the study, but *prior* to the initiation of placebo/selumetinib therapy.

14.31 Label the specimen tube with protocol number, ACCRU subject ID number, and time and date blood is drawn.

14.32 Ship the EDTA tube with a properly prepared cold pack.

14.33 Ship specimens via FedEx Priority Overnight service.

14.34 Ship samples to:  
BAP Freezer  
  
  

14.35 BAP Receiving will receive the samples and forward specimens to the ACCRU Research Base BAP Shared Resource, .

14.4 Study Methodology and Storage Information

14.41 Blood/blood product samples will be collected for the following research:

14.411 DNA extraction, storage, and analysis of DNA will be performed in BAP using standard laboratory protocols. These samples will be used as a normal control for the genomic analysis conducted upon the archival tumor tissue and may be analyzed in future pharmacogenetic assays. Remaining DNA will be stored frozen at -70°C by BAP, according to patient consent information until specific analyses are identified. As protocols are developed, they will be presented for ACCRU, IRB, and ITOG review and approval. (This collection is part of a general strategy of investigation for the majority of ACCRU/ITOG studies.)

14.412 As part of ongoing ACCRU/ITOG research, we will collect white blood cells/plasma for future research studies, according to patient consent information. Samples will be stored frozen at -70°C by BAP until specific analyses are identified. As protocols are developed, they will be presented for ACCRU, ITOG, and IRB review and approval.

14.5 Because the results generated by the genetic testing included in this section are not currently anticipated to have clinical relevance to the patient or their family members, the genetic results will not be disclosed to the patients or their physicians.

If, at any time, genetic results are obtained that may have clinical relevance, IRB review and approval will be sought regarding the most appropriate manner of disclosure and whether or not validation in a CLIA-certified setting will be required. Sharing of research data with individual patients should only occur when data have been validated by multiple studies and testing has been done in CLIA-approved laboratories.

## 15.0 Drug Information

**Investigator Brochure:** The most current version of the Investigator Brochure will be maintained in the study folder on the ACCRU website. Updated Investigator's Brochures should be obtained from the study folder as they become available.

Each investigator should obtain a copy of the Investigator's Brochure prior to initiation of the study.

15.1 Selumetinib (AZD6244 Koselugo™) or selumetinib-matched placebo

15.11 **Background:** The RAS/RAF/MEK/ERK pathway is an important mediator of many cellular processes including proliferation, survival, differentiation, apoptosis, motility and metabolism. This pathway is often aberrantly activated in human tumors due to the overexpression of activated K-RAS, mutant b-Raf, or other growth factor receptors. Selumetinib is a selective mitogen-activated protein kinase (MEK) inhibitor. By inhibiting MEK, selumetinib inhibits ERK phosphorylation. Thus, selumetinib may inhibit oncogenic growth signaling in tumor cells by targeting the RAS/RAF/MEK/ERK pathway.

15.12 **Formulation:**

The drug product consists of a series of plain, HPMC capsules containing 10 mg (white) and 25 mg (blue) selumetinib (expressed as free-base) for oral administration. Selumetinib capsules are supplied in white, HDPE bottles with desiccant, a tamper evident induction seal membrane and child resistant screw closure.

The 10 mg capsule is presented as either a plain white capsule with a center band, or white to off-white capsule with a center band marked with 'SEL 10' printed in black ink.

The 25 mg capsule is presented as either a plain blue capsule with a center band, or blue capsule with a center band marked with 'SEL 25' printed in black ink.

Apart from the markings, plain and marked capsules are identical in all other aspects.

The capsules contain selumetinib Hyd-Sulfate and Vitamin E polyethylene glycol succinate (also known as TPGS - a water soluble form of vitamin E)Placebo composition is consistent with the composition of drug product, with the absent drug substance being replaced by Vitamin E polyethylene glycol succinate. The same HPMC capsule shells are used for both placebo and active drug products.

Both selumetinib and placebo are supplied in 25 mg capsules in bottles containing 60 capsules each.

15.13 **Preparation and Storage:** Store the selumetinib or placebo capsules in the original packaging until use at room temperature (20° C-25° C). Brief excursions are permitted between 15° C and 30° C. For further information refer to the investigational product label.

15.14 **Administration:** Selumetinib should be taken on an empty stomach, 1 hour before or 2 hours after a meal. Take capsules with water only.

15.15 **Pharmacokinetic information:**  
**Absorption** - Selumetinib was absorbed relatively quickly across all dose levels, with a median  $t_{max}$  of 1 to 1.5hours across the dose range (25 to 100 mg).  
**Distribution** - Following the peak, selumetinib concentrations declined multi-exponentially, with a mean  $t_{1/2}$  ranging from 5 to 7 h, which is consistent across dose levels. CL/F and  $V_{ss}/F$  also remained largely consistent across the dose range, with mean values ranging from 12 to 23 L/h and 87 to 126 L respectively. Plasma N-desmethyl selumetinib concentrations followed a similar pharmacokinetic profile to selumetinib, although exposure was much lower, with  $C_{max}$  and AUC values generally <15% of parent, within each patient. The median  $t_{max}$  was around 1.5 hrs and  $t_{1/2}$  was around 9 to 13 hours.

#### **Metabolism -**

Cytochrome P450 3A4 is the predominant isoform responsible for selumetinib oxidative metabolism with CYP2C19, CYP1A2, CYP2C9, CYP2E1, and CYP3A5 involved to a lesser extent. Its active metabolite, N-desmethyl selumetinib is approximately 3-5 times more potent than selumetinib, and generated primarily by CYP1A2, CYP2C19, CYP2C9 and CYP2C8 and metabolized through the same routes as selumetinib.

**Special Populations** – Renal impairment is expected to have minimal effect on exposure to selumetinib. Patients with moderate and severe hepatic impairment may experience higher exposures of approximately 1.5-and 3-fold, respectively. It is recommended that investigators take this information into consideration if patient experience moderate or severe hepatic impairment during the study treatment.

15.16 **Potential Drug Interactions:** High vitamin E doses may potentiate the anticoagulant activity of warfarin. Monitor PT/INR more frequently in patients receiving both selumetinib and warfarin.

The concomitant intake of supplemental vitamin E should be avoided in all subjects receiving selumetinib.

Avoid co-administering selumetinib with medicinal products that are strong inhibitors of CYP3A4 (eg, clarithromycin, grapefruit juice, oral ketoconazole) and CYP2C19 (eg, ticlopidine). If co-administration is unavoidable, patients should be carefully monitored for AEs. No dose adjustment is necessary for

use of selumetinib with moderate CYP3A4 or CYP2C19 inhibitors. Patients should be carefully monitored for AEs when co-administered with moderate CYP3A4 or CYP2C19 inhibitors.

Avoid concomitant use of strong CYP3A4 inducers (eg, phenytoin, rifampicin, carbamazepine, St. John's Wort) or moderate CYP3A4 inducers with selumetinib.

Selumetinib may be an inhibitor of OAT3 and the potential for a clinically relevant effect on the PK of concomitantly administered substrates of OAT3 cannot be excluded.

Based on *in vitro* data and SimCYP simulations, selumetinib is considered unlikely to cause clinically significant drug-drug interaction via inhibition or induction of CYP enzymes

#### 15.17 **Known potential toxicities:**

##### **Very Common Adverse Events, (>10%)**

Cardiovascular: Peripheral edema

Central nervous system: Fatigue, headache

Dermatologic: Rash acneiform, rash maculo-papular

Endocrine & metabolic: Creatine phosphokinase (CK) increased

Gastrointestinal: Diarrhea, nausea, vomiting, abdominal pain, constipation.

Respiratory: Exertional dyspnea

##### **Common Adverse Events, (1 to <10%)**

Cardiovascular: Hypertension

Central nervous system: Fever, dizziness, insomnia, depression

Dermatologic: Dry skin, pruritus, rash

Endocrine & metabolic: Hypoalbuminemia, hypomagnesemia, hyperphosphatemia

Eye: Periorbital edema, blurred vision

Gastrointestinal: upper abdominal pain, abdominal distension, stomatitis, anorexia, decreased appetite, dry mouth

Hematologic: Thrombocytopenia, anemia

Hepatic: AST increased, ALT increased

Neuromuscular & skeletal: Back pain, arthralgia, asthenia

Respiratory: Dyspnea, cough

Miscellaneous: Alopecia, Low blood potassium

##### **Rare Adverse Events (Important or life-threatening), <1%**

Left ventricular systolic dysfunction, Liver injury/failure

#### 15.18 **Drug procurement:**

AstraZeneca will supply selumetinib or placebo to Clinical Research Services, a division of Rx Crossroads by McKesson for distribution to participating sites. No blinded starter supplies will be available for this study. Blinded, patient-specific clinical supplies will be sent to the registering investigator at the time of randomization and should arrive within 3-5 days. This randomization will be performed by the ACCRU Statistical and Data Center. The assigned ACCRU Patient ID number must be recorded by the registering institution for proper bottle dispersion. Once a patient has been registered, ACCRU will electronically transmit a clinical

drug request for that patient to Clinical Research Services, a division of Rx Crossroads by McKesson. This request will be entered and transmitted by ACCRU the day the patient is registered and will be processed and shipped by Clinical Research Services, a division of Rx Crossroads by McKesson the same business day if received before 2 pm ET. If the request is received after 2 pm ET, drug will be shipped the following business day. Shipments will be sent via FedEx Priority Overnight.

If additional supplies are needed, contact a member of the Clinical Research Services team:

Clinical Research Services, a division of Rx Crossroads by McKesson  
Clinical Research Services  
[REDACTED]  
[REDACTED]  
[REDACTED]

*Outdated or remaining drug is to be destroyed on-site as per procedures in place at each institution.*

#### 15.19 **Nursing Guidelines**

- 15.191 Medication should be taken on an empty stomach with no food or drink other than water for 1 hour before and 2 hours after dosing.
- 15.192 Gastrointestinal side effects were the most commonly reported side effects with this agent (including nausea, diarrhea, constipation, dyspepsia and vomiting). Manage symptomatically and assess for effectiveness of intervention.
- 15.193 Patients experienced acneiform rash. Instruct patient to report this rash and manage symptomatically.
- 15.194 Dyspnea has been reported. Instruct patient to report any shortness of breath to the study team. Rarely interstitial lung disease has been seen with agent.
- 15.195 Hypertension has been seen. Assess blood pressure according to study requirements.
- 15.196 Instruct patients to report any limb swelling (usually legs) to the study team. Rarely LVEF dysfunction has been seen.
- 15.197 Monitor LFT's.
- 15.198 Monitor CBC w/diff. Instruct patients to report any unusual bruising or bleeding to the study team.
- 15.199a Patients may experience increased fatigue. Instruct patients in energy conserving lifestyle.
- 15.199b Warn patients of possible alopecia.
- 15.199c Instruct patients to report any blurred vision or periorbital edema to the

study team.

15.199d Assess patient's concomitant medications as there are numerous drug to drug interactions.

15.2 Thyrogen™ (rhTSH, thyrotropin alfa for injection)

Effective conduct of RAI therapy requires stimulation by TSH in order to maximize RAI uptake by thyroid cells. Recombinant human TSH (rhTSH or Thyrogen™) will be used to stimulate iodide uptake according to the manufacturer's recommendation (0.9 mg intra-muscular injection for 2 days prior to the RAI administration according to the Section 4.0). This allows patients to avoid the hypothyroidism state, since they can maintain their routine thyroid hormone supplementation. Patients or clinicians choosing withdrawal of thyroid hormone treatment for this purpose will be ineligible for this study.

15.21 **Drug procurement:** Commercial supplies. Pharmacies or clinics shall obtain supplies from normal commercial supply chain or wholesaler.

15.3 Radioactive iodine (RAI)

15.31 Therapeutic RAI dose ( $^{131}\text{I}$ )

Patients  $<70$  years of age will be treated with 150 mCi  $^{131}\text{I}$  ( $+/-.5$  mCi). Patients  $\geq 70$  years of age can be treated with a  $^{131}\text{I}$  activity from 100 mCi up to and including 150 mCi ( $+/-.5$  mCi for 100 mCi or 150 mCi administered activities); for these patients, the activity to be administered must be determined by the investigator at the time of study registration.

Though performing whole blood and body dosimetry to determine maximum tolerated activity (MTA) is NOT required, for centers at which this evaluation *is* done prior to therapeutic  $^{131}\text{I}$  study administration (Week 4), lower  $^{131}\text{I}$  activities than what is recommended here may be administered if the MTA is calculated to be lower than the lower limit of what is allowed per protocol or what has been determined to be given (for patients  $\geq 70$  years of age). **Examples** (these are applicable only in instances in which dosimetry was performed prior to therapeutic  $^{131}\text{I}$  administration): 1) *Patients <70 years of age:* If the dosimetry-determined MTA value is less than 150 mCi, then a RAI activity less than 150 mCi may be administered; 2) *Patients >70 years of age:* If the dosimetry-determined MTA value is less than the activity that was determined to be given at the time of study registration, then a lower RAI activity may be administered, even activities less than 100 mCi if the MTA is below this threshold. Dosimetry can NOT be used to justify administering therapeutic  $^{131}\text{I}$  activities higher than what has been recommended per this protocol.

Administration of Thyrogen™ and/or therapeutic  $^{131}\text{I}$  at a facility other than the participating site is allowed if documentation of the dates and amount/activity of drug /radioisotope administered is provided to verify adherence to protocol requirements.

Any form of oral  $^{131}\text{I}$  (e.g., capsule or liquid) is allowed.

15.32 **Drug procurement:** Commercial supplies. Pharmacies or clinics shall obtain supplies from normal commercial supply chain or wholesaler.

16.0 Statistical Considerations and Methodology

## 16.1 Study Overview

This randomized, double-blind Phase II trial will compare the response rate at 6 months after therapy with  $^{131}\text{I}$  in combination with placebo or selumetinib for the treatment of patients with RAI A recurrent and/or metastatic thyroid cancer. Historical response rate to a single dose of RAI can be difficult to estimate from retrospective data that include heterogeneity with regards to the extent of disease treated, RAI doses administered, patient preparation, response assessments etc. Nonetheless, a retrospective analysis has demonstrated that the response rate for first-line  $^{131}\text{I}$  therapy alone for recurrent/metastatic RAI A thyroid cancer with measurable disease is generally around 20% (Sabra et al., 2013). We estimate that patients with non-measurable disease and with the serum thyroglobulin criteria described in this protocol will have a response rate of approximately 50%. Anticipating that 40% of the patients accrued will have measurable disease and 60% with non-measurable disease only (requiring serum TG measurements to be used in response assessment), the predicted response rate for this population would be 40%. It is hoped that the combination of selumetinib and  $^{131}\text{I}$  can increase the response rate to 65%.

This trial will also compare the best overall response rate, progression-free survival (PFS), changes in serum thyroglobulin levels and adverse event rates between the two treatment arms. In addition, we will explore the genomic and transcriptomic landscape of RAI A tumors for signatures that correlate to therapeutic benefit achieved in patients with RAI-avid recurrent and/or metastatic thyroid cancer treated with  $^{131}\text{I}$  in combination with placebo or selumetinib.

## 16.2 Primary Endpoint

The primary endpoint for this study will compare the response rate with  $^{131}\text{I}$  in combination with placebo or selumetinib for the treatment of patients with RAI A recurrent and/or metastatic thyroid cancer at the 6-month time point (“6-month time point” refers to the assessments designated to occur approximately 6 months after  $^{131}\text{I}$  therapy in combination with placebo or selumetinib has been administered, which may be 6 months +/- 1 week from the time therapeutic RAI is administered. For patients with non-measurable disease, TG values obtained outside this window may be allowed if repeat measurements were required to ensure the this value was obtained in the context of a TSH  $\leq 0.4$ ).

A patient will be classified as a responder if they have a partial or complete response at the 6-month time point when compared to the baseline, pre-study radiologic scan(s) according to the criteria outlined in Section 11.0 (confirmation of response is not required). The proportion of patients with a response will be calculated and compared between the 2 arms using a Chi-square or Fisher’s Exact test. All eligible patients who are randomized and begin treatment will be evaluable for the primary endpoint.

It is possible that patients will have clinical, radiologic, or biochemical evidence of disease progression early in the study and still demonstrate benefit from the study treatment later in the study for several reasons: 1) selumetinib alone prior to RAI may not have significant clinical efficacy, 2) Thyrogen™ stimulation can transiently increase tumor size which can be mistaken for disease progression; 3) the therapeutic effects of RAI can be delayed; and 4) evidence of progression may be evident prior to administration of RAI. Hence, patients with evidence of radiographic or clinical PD noted prior to the 6-month time point assessment may remain on study and continue to receive treatment and/or be evaluated for response at the discretion of the treating physician. The final objective response assessment at 6 months for these patients will be based upon a comparison between the 6-month radiologic scan(s) (and serum thyroglobulin,

if applicable) and the baseline, pre-study radiologic scans (and serum thyroglobulin, if applicable). However, if in the opinion of the treating physician these patients are unlikely to demonstrate benefit at the 6-month time point, the patients will be considered to have had a progression/death event, categorized as non-responders, and taken off the study.

Patients who receive additional treatment for their thyroid cancer outside of this protocol prior to the 6-month time point (except for thyroid hormone TSH suppression, palliative radiation to a non-target lesion, or therapy to prevent pathologic fractures caused by bone metastases (e.g. zoledronic acid and denosumab)) will be considered non-responders.

**Final Analysis for Primary Endpoint:** The primary goal is to compare  $^{131}\text{I}$  in combination with placebo or selumetinib where the alternative hypothesis is that selumetinib and  $^{131}\text{I}$  has an improved confirmed response rate compared to placebo plus  $^{131}\text{I}$ . Twenty-eight evaluable patients will be enrolled to each arm, for 56 evaluable patients, total. With this sample size, we will be able to detect a significant difference between a response rate of 40% in the control group vs. 65% in the experimental group (odds ratio for response of 2.786, with 1-sided type I error = 0.15 and power = 80%). All patients who meet the eligibility criteria, sign the consent form, are randomized, and start treatment will be evaluable.

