## 5.0 Stratification Factors:

This Phase 2 randomized study will compare radioactive iodine (RAI) in combination with placebo or selumetinib for the treatment of RAI-avid recurrent/metastatic thyroid cancers. A 1:1 randomization will be used, where the Pocock-Simon algorithm (Pocock SJ et al, 1975) will be used to balance the arms with respect to the following stratification factors, along with the registering membership:

- Prior thyroid cancer treatment with systemic chemotherapy and/or molecularly targeted inhibitors: Yes vs. No
- Age  $\geq 70$  years: Yes vs. No
- Bone Metastases present: Yes vs. No
- Previous  $^{131}\text{I}$  therapy given for thyroid remnant ablation prior to this study: Yes vs. No
- Measureable disease (as defined by this protocol): Yes or No

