6.2 Randomization Procedures

6.21 The factors defined in Section 5.0, together with the registering membership, will be used as stratification factors.

6.22 After the patient has been registered into the study, the values of the stratification factors will be recorded, and the patient will be assigned to one of the following treatment groups using the Pocock and Simon dynamic allocation procedure which balances the marginal distributions of the stratification factors between the treatment

groups (Pocock-Simon ref – see below).

- Radioactive iodine (RAI) plus placebo
- Radioactive iodine plus selumetinib

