#### 11.434 Overall Objective Status for Patients with Measureable Target Lesions/Lymph Nodes

The overall objective status for an evaluation is determined by combining the patient's status on target lesions, target lymph nodes, non-target lesions, non-target lymph nodes, and new disease as defined in the following tables. Serum thyroglobulin measurements will not be used in determining overall response, except for designating a complete response (as detailed in Section 11.432 and in the table below):

Target Lesions & Target Lymph Nodes	Non-Target Lesions & Non-Target Lymph Nodes	New Sites of Disease	Overall Objective Status
CR	CR	No	CR*
CR	Non-CR/Non-PD	No	PR
PR	CR Non-CR/Non-PD	No	PR
CR/PR	Not All Evaluated**	No	PR***
SD	CR Non-CR/Non-PD Not All Evaluated**	No	SD
Not all Evaluated	CR Non-CR/Non-PD* Not All Evaluated**	No	Not Evaluated (NE)
PD	Unequivocal PD CR Non-CR/Non-PD Not All Evaluated**	Yes or No	PD
CR/PR/SD/PD/Not all Evaluated	Unequivocal PD	Yes or No	PD
CR/PR/SD/PD/Not all Evaluated	CR Non-CR/Non-PD Not All Evaluated**	Yes	PD

\* CR designation may also require serum thyroglobulin assessment as detailed in Section 11.432.

\*\* See Section 11.431

\*\*\* NOTE: This study uses the protocol RECIST v1.1 template dated 2/16/2011. For data collection and analysis purposes the objective status changed from SD to PR in the ACCRU protocol RECIST v1.1 template as of 2/16/2011 and to match RECIST v1.1 requirements.

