#### **Overall Objective Status for Patients with Non-Measurable, Non-Target Lesions/Lymph nodes**

The overall objective status for an evaluation is determined by:

- Structural assessment of lesions/lymph nodes as detailed in Section 11.442.
- For the “non-CR/non-PD” structural category, measurement of the serum TG in the context of suppressed TSH (and negative TG antibody) will be used to determine the final response designation (the exception is for the assessment of complete response, which requires measurement of a stimulated TG, see chart below).

Non-Target Lesions & Non-Target Lymph Nodes	Serum Thyroglobulin (TG)* (or TG antibody)	New Sites of Disease	Overall Objective Status
CR	TG < 0.2 ng/ml on TSH suppression* OR stimulated TG < 0.1 ng/ml (see 11.442)	No	CR
CR	TG ≥ 0.2 ng/ml on TSH suppression* OR stimulated TG > 0.1 ng/ml (see 11.442)	No	Assess as per Non-CR/Non-PD
Non-CR/Non-PD	50% or more reduction compared to baseline Tg WITHOUT a 25% or more increase compared to the lowest TG measured on study (baseline or nadir)*	No	PR
Non-CR/Non-PD	25% or more increase compared to the lowest TG measured on study* (baseline or nadir)	No	PD
Non-CR/Non-PD	Less than 50% reduction compared to baseline TG WITHOUT a 25% or more increase compared to the lowest TG measured on study* (baseline or nadir)	No	SD
Non-CR/Non-PD	New detection of TG antibody	No	PD
Not All Evaluated	25% or more increase compared to lowest TG measured on study Tg* (baseline or nadir)	No	PD

Non-Target Lesions & Non-Target Lymph Nodes	Serum Thyroglobulin (TG)* (or TG antibody)	New Sites of Disease	Overall Objective Status
Not All Evaluated	WITHOUT 25% or more increase compared to lowest TG measured on study Tg* (baseline or nadir)	No	NE
Uequivocal PD	Any serum TG result or TG antibody result, including failure to complete the measurement as per protocol	Yes or No	PD
CR Non-CR/Non-PD Not All Evaluated	Any serum TG or TG antibody result, including failure to complete the measurement as per protocol	Yes	PD
CR Non-CR/Non-PD Not All Evaluated	TG was not evaluated or not evaluated in the context of TSH suppression*	No	NE

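### The primary test is left as an unstratified chi-square or Fisher's exact test with no rule; name one, preferably a one-sided CMH test stratified by measurable disease

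*Combined protocol and SAP*

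**What the plan says.** Section 16.2 describes the primary comparison of 6-month response in one sentence: "The proportion of patients with a response will be calculated and compared between the 2 arms using a Chi-square or" Fisher's exact test. It gives no selection rule, no statement on continuity correction and no stratification. The final-analysis paragraph of the same section sets 28 evaluable patients per arm, 40% versus 65%, an odds ratio of 2.786, one-sided type I error 0.15 and 80% power, but does not say which test these belong to. Section 16.3 names chi-square alone for best overall response and repeats the either/or wording for adverse events.

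Section 5.0 lists among the balancing factors "Measureable disease (as defined by this protocol): Yes or No". Section 6.22 assigns patients by a Pocock-Simon "dynamic allocation procedure which balances the marginal distributions of the stratification factors between the treatment" groups.

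The two disease groups are scored differently. For measurable disease (11.434), "Serum thyroglobulin measurements will not be used in determining overall response, except for designating a complete response". For patients with non-measurable disease only (11.443), in the category that is neither complete response nor progression, "measurement of the serum TG in the context of suppressed TSH (and negative TG antibody) will be used to determine the final response designation".

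Section 16.1 says the response to radioiodine alone "with measurable disease is generally around 20" per cent, and that patients with non-measurable disease "will have a response rate of approximately 50" per cent. On the mix it says: "Anticipating that 40% of the patients accrued will have measurable disease and 60% with non-measurable disease only".

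**The concern.** There are two separate issues.

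First, the primary test is not fixed. Chi-square and Fisher are not interchangeable at 28 per arm: Fisher is the more conservative, and the plan's sample size may have been built on only one of them. A result near the boundary could then be called positive or negative according to a choice made after the data are seen.

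Second, neither test uses a factor that the plan itself expects to separate 20% from 50% response and already balances in the randomisation. Marginal balancing makes imbalance on that factor smaller but does not remove it. If one arm happens to hold more non-measurable patients, it has a higher expected response rate with no drug effect, and an unstratified test counts that as evidence.

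**Working it through.** **Inputs.** From 16.2: 28 per arm, 40% versus 65%, one-sided 0.15, 80% power. From 16.1: control rates of 20% (measurable) and 50% (non-measurable), 40/60 mix, so about 11 measurable of 28 per arm. The mix gives 0.4 × 20% + 0.6 × 50% = 38%, which the plan rounds to 40%.

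**Step 1. Reproduce the plan's figure.** The odds ratio is (0.65/0.35)/(0.40/0.60) = 2.786. With the pooled formula, p̄ = 0.525:

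n = [1.036·√(2 × 0.525 × 0.475) + 0.842·√(0.40 × 0.60 + 0.65 × 0.35)]² / 0.25² = 27.3, so 28 per arm.

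This matches. A continuity correction gives 34.9 (35 per arm), and Fisher's exact power first reaches 80% at 36 per arm. The sizing is therefore that of an uncorrected chi-square.

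**Step 2. Compare the two permitted tests.** All 29 × 29 outcomes were enumerated.

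| | Uncorrected chi-square | Fisher |
|---|---|---|
| Size at a common 40% | 17.0% | 11.0% |
| Largest size over common rates | 18.0% | 11.4% |
| Power, 40% versus 65% | 83.4% | 75.7% |

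A continuity-corrected chi-square has the same size and power as Fisher here. With 4 to 20 control responders, the uncorrected chi-square needs 4 more responders on selumetinib and Fisher needs 5. For 15/28 versus 11/28, p̄ = 26/56 and z = 0.1429/√(2 × 0.4643 × 0.5357/28) = 1.07, so p = 0.142; Fisher gives 0.211. The design expects about 11 control responders (40% of 28). The tests give opposite verdicts with probability 6.0% at a common 40% and 7.7% at 40% versus 65%.

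**Step 3. Condition on the split of measurable disease.** With no drug effect and rates of 20% and 50% in both arms, exact enumeration by stratum and arm was used. The CMH statistic is z = Σ(aₖ − n₁ₖmₖ/Nₖ)/√ΣVₖ, with Vₖ = n₁ₖn₀ₖmₖ(Nₖ − mₖ)/[Nₖ²(Nₖ − 1)]. Here aₖ is selumetinib responders, mₖ all responders, n₁ₖ and n₀ₖ the arm sizes and Nₖ the total in stratum k. No continuity correction is applied.

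| Measurable, selumetinib vs placebo | Chi-square size | CMH size |
|---|---|---|
| 9 vs 13 | 25.4% | 15.1% |
| 10 vs 12 | 20.1% | 14.0% |
| 10 vs 11 | 17.9% | 16.2% |
| 11 vs 11 | 15.6% | 15.6% |
| 11 vs 10 | 13.7% | 14.7% |
| 12 vs 10 | 11.8% | 15.2% |
| 13 vs 9 | 8.7% | 14.9% |

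Over all 59 splits with 16 to 28 measurable patients in total and arms differing by at most 4, chi-square runs from 8.2% to 25.8% and CMH from 14.0% to 16.6%.

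**Step 4. How often imbalance occurs.** The documents give neither the allocation probability nor the factor prevalences, so this is assumed. Pocock-Simon allocation was simulated with a biased coin of 0.7 to 1.0, 6 or 15 memberships and two prevalence sets, 20,000 trials each. The arms differ by 2 in 28 or more in 42% (coin 0.7) down to 14% (coin 1.0) of trials, and by 4 or more in 13% down to 1%. Half of these favour selumetinib.

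**Step 5. Power of CMH at 11 versus 11.**

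| Assumed effect within groups | Selumetinib rates (measurable/non-measurable) | Overall | Power |
|---|---|---|---|
| Odds ratio 2.786 | 41.1%/73.6% | about 61% | 79.4% |
| +25 points in each group | 45%/75% | 63% | 84.5% |
| Odds ratio 3.44 | 46.3%/77.5% | 65% | 88.2% |

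At odds ratio 3.44, chi-square versus CMH power is 89.9% versus 86.4% at 10 vs 11, 94.0% versus 86.2% at 9 vs 13, and 79.4% versus 86.6% at 13 vs 9.

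**The case against.** The best defence on the first issue is convention: Fisher is commonly kept for small expected counts. Under a below-5 rule it would apply in only 0.01% of trials at 40%, so chi-square would in effect be the test. But the plan does not state such a rule, and one sentence would settle it.

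On the second issue, the unstratified chi-square is not invalid. Measurable disease is already handled in the design. Averaged over splits differing by at most 2, weighted by binomial probabilities, chi-square size is 15.8% and CMH 15.2%; at odds ratio 3.44, power is 88.0% and 86.9%. The wide range in step 3 comes from differences of 4, which are uncommon. The effect also depends on the 20% and 50% rates, and 16.1 offers the 50% only as an estimate. With control rates of 30% and 47%, chi-square size at 9 vs 13, 10 vs 12 and 12 vs 10 is 21.8%, 19.1% and 14.4%; with 35% and 43% it is 19.2%, 18.0% and 15.8%. At a common 40% it is 17.0% at any split, so part of the excess is discreteness and not imbalance.

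CMH is not exact either. At 11 vs 11 its size runs from 14.3% to 17.5% over a grid of null rates, whereas Fisher's stays below 15% at any common rate. CMH power also falls short of 80% at a within-group odds ratio of 2.786: 79.4% at 11 vs 11 and 76.5% at 10 vs 12.

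All of this stands. It makes stratification an improvement and not the repair of an invalid test, and it leaves the sponsor a real trade between size and power. It does not justify leaving the primary test open.

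**Conclusion.** The concern holds. The plan permits two primary tests that disagree on a 4-responder difference in the centre of its design range, and only the uncorrected chi-square matches the stated 28 per arm and 80% power. This rests on the plan's own figures and on no outside assumption.

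Stratifying by measurable disease is the better choice because it removes most of the dependence of the error rate on how that factor happens to split. Under the plan's 20% and 50% rates, a split of 10 versus 12 in either direction moves chi-square size between 11.8% and 20.1%, against 14.0% to 15.2% for CMH. The gain is smaller if the two groups respond more alike, and how often it matters depends on allocation details that the documents do not give. The price is lower power than chi-square when imbalance favours selumetinib, where chi-square's extra power comes with inflated size. The change should be made; it does not call the sample size into question.

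**What to change.** In 16.2, name one primary test: a one-sided asymptotic Cochran-Mantel-Haenszel test without continuity correction, stratified by measurable disease as recorded at randomisation, at 0.15. Report the stratified risk difference with its interval. Keep the uncorrected chi-square as a sensitivity analysis. Lack of correction should be explicit, because the corrected CMH is conservative (size 9.7% at 11 vs 11).

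If the sponsor prefers an unstratified primary test, name the uncorrected chi-square, which the sizing implies, and acknowledge its size of 17.0% at a common 40%.

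Either way, restate size and power for the named test over a range of within-group effects such as those in step 5. The documents give only the overall 40% versus 65%, so the within-group pattern is an assumption and should be labelled as one.

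The cost is wording in 16.2 and a short recalculation, to be fixed before unblinding. The factor is already recorded at randomisation, so no extra patients or data are needed. The statistical cost is the power given up when chance imbalance favours selumetinib.
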